### 5.3 Follow-Up Assessments

The Investigator will also inform the subject's local doctor / General Practitioner (GP) in writing of the subject's participation in this investigation at the same time as advising of the surgical procedure, providing the subject gives their consent to this process.

Subjects will be followed up as part of the clinical investigation at the following time points (date range for acceptable time window):

- Discharge/immediate post-operative (0-10 days)
- 3 months (35-126 days OR 5-18 weeks) post treatment
- 12 months (281-449 days OR 40-64 weeks) post treatment
- 24 months (646-1644 days OR 92-234 weeks) post treatment
- 60 months (1645-2005 days OR 235-286 weeks) post treatment
- 120 months (3470-3830 days OR 495-547 weeks) post treatment

All follow-up assessments and applicable unscheduled (*i.e.*, unplanned or unscheduled that occur between the protocol defined visit windows) visits will be recorded in the subject's eCRF by the Investigator study team unless otherwise indicated.

Both study and unscheduled office visits are defined as any visit at the study site where a study subject is seen by one of the site staff including the Principal Investigator (PI), any Sub-investigator (as appropriate), or anyone identified on the PI's team/delegation of authority.

An unscheduled visit is to be documented on an Unscheduled Visit eCRF/CRF when:

1. A subject returns for an additional visit during a study visit interval as described in **Table 1 - Time and Events**.
2. A subject returns between study visit intervals

If the previous protocol-defined study interval visit was missed, the required eCRFs/CRFs in the previously missed interval visit are also required to be completed along with the Unscheduled Visit eCRF.

If an unscheduled visit is related to a new, worsening, or resolved adverse event, both an AE eCRF and the Unscheduled Visit eCRF are to be completed.

**Important note:** Adverse Event (AE), including serious AEs, information is to be collected at ALL interactions with the study subject. This includes when non-site staff treats the study subject in a manner where the source documentation is available to the site staff. The site staff is responsible to review the medical event and report it per the protocol.

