### 5.3.2 Radiographic Assessments

Radiographs will be taken at the following time points:

- Immediate post-operative (0-10 days) – only Grashey AP view required
- 3, 12, 24, 60 and 120 months post treatment – Grashey AP and Axillary view required

The investigator will not be required to complete any eCRF's for per protocol radiographic assessments.

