1.3 Secondary Objectives

Secondary objectives include the assessment of clinical and radiographic performance post-operatively at 3-, 12-, 24-, 60- and 120-month visits. Assessments include: adjusted Constant-Murley Score, Oxford Shoulder Score, EQ-5D-5L and radiographic evidence of aseptic loosening of the GLOBAL ICON stemless humeral component. Of interest for the non-radiographic endpoints are mean values at the distinct time points. Based on radiographic data, time to aseptic loosening will be characterized by survival analysis using Kaplan-Meier methodology, where the event of interest is aseptic loosening. Survival will be reported at the last day of each assessment window.

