9.7 Modeling of the Secondary and Tertiary Endpoints

Confidence intervals (95%) and p-values will be based on means at each time point using a one sample t-test; change from baseline summaries will also be provided in this fashion.

In addition, for analyses which involve change from baseline (tertiary endpoints), each TV-eFRM 02880

post-surgical measurement will be represented as a change from baseline, with baseline measurement and other possible factors of interest included as covariates in a linear regression model. These analyses are deemed exploratory, with no adjustment for multiplicity and no labeling claims based on the results. PROC TTEST and PROC REG will be used for the analyses. As noted in 9.8.4, the analysis is repeated in each imputed data set and thereafter aggregated. Aggregated results will be reported.

The Kaplan-Meier methods will be used to report results for survival endpoints. Survivorship point estimates and 95% confidence intervals will be presented for a time point if at least 40 subjects remain at risk. The conventional Greenwood estimate will be used to calculate the variance and the complementary log-log transformation will be used to construct 95% confidence intervals using PROC LIFETEST.

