9.8.2 Survival Endpoints

Safety, secondary and tertiary endpoints include survival outcomes. Patients with missing data resulting from withdrawal will be treated as censored, with their censoring time based on the date of last assessment.

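### Film-detected aseptic loosening is analysed by right-censored Kaplan-Meier read at the end of each window, which flatters the 24-month figure and leaves no usable 120-month figure

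*SAP*

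**What the plan says.** Protocol 5.3.2 sets the film schedule: "Radiographs will be taken at the following time points", namely immediately after surgery and then "3, 12, 24, 60 and 120 months post treatment". Protocol Table 1 also allows films at unscheduled visits. The windows in Protocol 5.3 include "24 months (646-1644 days OR 92-234 weeks) post treatment" and "60 months (1645-2005 days OR 235-286 weeks) post treatment"; the 120-month window is days 3470 to 3830. SAP section 4 has the same windows.

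SAP 1.3 says that "time to aseptic loosening will be characterized by survival analysis using Kaplan-Meier methodology, where the event of interest is aseptic loosening", and the next sentence fixes where the curve is read: "Survival will be reported at the last day of each assessment window". SAP 9.7 repeats the method ("The Kaplan-Meier methods will be used to report results for survival endpoints"), using PROC LIFETEST with Greenwood variance, and shows an estimate only where at least 40 subjects remain at risk. SAP 9.8.2 censors withdrawn subjects, "with their censoring time based on the date of last assessment".

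Protocol 7.9.3 also promises the number and percentage with loosening at each planned visit, alongside the survival estimates. Neither document gives an event date for loosening found on a film, and neither mentions interval censoring.

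**The concern.** A first positive film places the onset of loosening somewhere after the last negative film. Between the 60- and 120-month films that interval is 3650 − 1825 = 1825 days (5.0 years) nominally, and up to 3830 − 1645 = 2185 days (6.0 years) by the windows. Kaplan-Meier for right-censored data needs a date of onset. If the film date is used, two errors follow:

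- Between visits, subjects who have already loosened count as event-free, so the curve is too high.
- In the last window with films, event-free subjects are censored on their film dates while others have events on theirs. The risk set runs down to zero, each late event takes too large a step, and the curve falls too low.

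The error therefore depends on the day at which the curve is read. In an uncontrolled study of a stemless implant, absolute estimates such as this are the result. This is the only radiographic time-to-event endpoint.

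**Working it through.** **Inputs from the documents.** 157 subjects; the film windows above; reading days 1644, 2005 and 3830; the 40-at-risk rule. The documents give no loosening rate, so there is no planned figure to reproduce.

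**Assumptions.** Loosening of 10% by day 3650 (5% and 20% as a range); constant hazard, so true survival is S(t) = (1 − c)^(t/3650), where c is 10-year loosening; event on the date of the first positive film; other subjects censored at their last film; no unscheduled films.

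**Day 1644 by hand.** If 24-month films fall near day 730, no further film arrives until day 1645. The curve at day 1644 then simply carries survival at day 730:

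- c = 10%: 0.9^(730/3650) = 97.9%, against 0.9^(1644/3650) = 95.4%. Overstated by 2.5 points.
- c = 20%: 95.6% against 90.4%. Overstated by 5.2 points.
- c = 5%: 99.0% against 97.7%. Overstated by 1.3 points.

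**Day 3830 by hand.** Let n subjects enter the last window and let each film be positive with probability q. On average the curve is multiplied by the product of (1 − q/k) over k = 1 to n. With c = 10%, q = 1 − 0.9^(1825/3650) = 0.0513. With n = 149 the product is 0.749, and 0.749 × 94.8% (the Kaplan-Meier value at day 2005, below) = 71.0%. The truth is 0.9^(3830/3650) = 89.5%.

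**Simulation, 157 subjects, c = 10%.** Scenario A: full follow-up, 24-month films at days 646 to 814 (1,000 replicates). Scenario B: film attendance 95/90/85/75/60% and 40% of 24-month films after day 814 (2,000 replicates).

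| Day | Truth % | Kaplan-Meier A % | Kaplan-Meier B % | At risk A / B |
|---|---|---|---|---|
| 730 | 97.9 | 98.5 | 98.8 | 155 / 149 |
| 1644 | 95.4 | 97.9 | 97.5 | 154 / 138 |
| 1825 | 94.9 | 96.5 | 96.4 | 151 / 114 |
| 2005 | 94.4 | 94.8 | 94.7 | 149 / 90 |
| 3650 | 90.0 | 91.6 | 91.1 | 74 / 45 |
| 3830 | 89.5 | 69.0 | 69.7 | 0 / 0 |

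- **SAP reading days:** +2.5 and +2.1 points at day 1644; +0.4 and +0.3 at day 2005; −20.5 and −19.8 at day 3830. A further run reached 98.1% at day 1644 (+2.7).
- **Nominal days:** +0.6 to +1.6 points.
- **c = 20%:** day 1644 is +5.2 (A) and +4.4 (B). In A, day 2005 is 89.4% against 88.5%, and day 3830 is 48.1% against 79.1%.

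**Sensitivity (c = 10%, attrition of about 15% by 24 months, then 15% and 20%).**

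- 24-month films spread evenly over days 646 to 1644: the day-1644 error falls to 96.5 − 95.4 = 1.1 points.
- Weibull shape 0.5 and 2: day 1644 is +2.0 and +1.7 points; day 2005 is within 0.3; day 3830 is 78.5% against 89.8% and 65.0% against 89.0%.
- Data stopping at the 24-month film: nobody is at risk at day 1644, and the value there is too low (82.4% to 93.2% against 95.4%).

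**Interval-censored alternatives.** A Weibull interval-censored fit in scenario A gives 97.9, 95.4, 94.9, 94.4, 89.8 and 89.3% on the six days, within 0.2 points of the truth throughout. The Turnbull estimator was within about 0.6 points at days 730, 1825 and 3650, but it also falls too low at day 3830 (about 77%).

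**The case against.** The strongest reply is that the SAP reads the curve at the end of each window, when that visit's films are in. This largely works at 60 months. At 24 months, if films are on time, the value is correct for survival at day 730; it is wrong only as survival on day 1644, the day for which the SAP reports it. At 120 months the 40-at-risk rule would stop the collapsed figure from being printed. All of this stands, and it rules out a stronger reading that a reader might infer, namely that loosening-free survival is overstated at 24, 60 and 120 months alike. That pattern appears only at the nominal days, which are not the SAP's reading days.

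It is also fair that the event date is inferred, that unscheduled films would narrow some intervals, that visit percentages are reported anyway, and that SAP section 6 calls secondary objectives exploratory and bars labelling claims from them. Sampling error is of similar size: with all 157 followed, one binomial standard error at 95.4% is √(0.954 × 0.046/157) = 1.7 points.

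None of this supplies a 120-month survival estimate, which Protocol 7.9.3 promises, and sampling error does not excuse a systematic one.

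**Conclusion.** The concern holds in a limited form. The estimator does not match the data, and the effect differs by visit. With 10% loosening at 10 years and constant hazard, the reported 24-month value overstates survival on day 1644 by about 2 to 2.7 points (4 to 5 at 20% loosening; about 1 if films are spread evenly over the window). The 60-month value is right to about 0.3 or 0.4 points. The 120-month value is suppressed, or about 20 points too low if computed. Read at the nominal days, Kaplan-Meier would overstate by roughly 1 to 1.5 points.

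The sizes rest on assumed loosening rates, hazard, attendance and film timing, and on film dates serving as event and censoring dates. The 24-month overstatement also requires that later films are in the data. The mechanism does not depend on the rates chosen. The primary endpoint uses a binary film criterion at 24 months and is untouched.

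**What to change.** In SAP 1.3 and 9.7:

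- Analyse loosening as interval-censored: (last negative film, first positive film] for events, and (last negative film, infinity) for everyone else, with unscheduled films included. This also settles the missing event-date rule.
- Use a piecewise-exponential interval-censored model or the Turnbull estimator (PROC ICLIFETEST).
- Report survival with 95% confidence intervals at days 730, 1825 and 3650, not at the last day of each window. The reading day matters even after the change of method, because the Turnbull estimate also drops at day 3830.
- State how the 40-at-risk rule applies to interval-censored data, for example as the number with a film in or after that visit's window.
- Keep Kaplan-Meier for component removal, which has an exact date.

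The cost is SAP wording and one different procedure on film dates already collected. Intervals may be slightly wider, and the piecewise model adds a mild assumption about the hazard between films.

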1.4 Tertiary Objectives

Tertiary objectives are to evaluate levels of improvement, evaluated as a change from baseline for each post-operative assessment time point, for the adjusted Constant-Murley Score, Oxford Shoulder Score and EQ-5D-5L. This will be evaluated by examining change from baseline at 3-, 12-, 24-, 60-, and 120- month visits. Lastly, survival of the GLOBAL ICON stemless humeral component for the reason of periprosthetic fracture will be reported using Kaplan-Meier methodology. Survival will be reported on the last day of the 24-, 60- and 120-month assessment windows.

2. Treatment Assignment

Treatment assignment is described in Section 1.

3. Randomization and Blinding

Neither randomization nor blinding will be implemented in this study.

4. Interval Windows

Data collected throughout the study will be assessed for compliance with the protocol-specified visit schedule.

Table Seven windows are defined based on the number of days prior to or after surgery (Day 0): baseline, Immediate post-op, 3-months post-op, 12-months post-op, 24-months post-op, 60-months post-op and 120-months post-op. If multiple visits fall into the same interval, the result latest in the visit window with complete data will be used in the analysis.

Table 1. Interval Windows

Analysis Visit	Study Visit	Study Interval (Days from Surgery)	Visit Window
Baseline	Pre-Op	-180 days to day of surgery (day 0)	-180 to 0 days
Surgery	Surgery	0	
Immediate Post-Op	Immediate Post-Op	0-10	5 (-5 to +5 days)
3 Months	3 Months	35 – 126	80 ± 45 days
12 Months	12 Months	281 – 449	365 ± 84 days
24 Months	24 Months	646 - 1644	730 - 84 days 730 + 914 days
60 Months	60 Months	1645 - 2005	1825 ± 180 days
120 Months	120 Months	3470 – 3830	3650 ± 180 days

5. Description of Scales and Scoring

The Constant-Murley score (CMS) is a 100-points scale composed of a number of individual parameters. These parameters define the level of pain and the ability to carry out the normal daily activities of the patient. The Constant-Murley score was used to determine the functionality after the treatment of a shoulder injury. It has four subscales: pain (15 points), activities of daily living (20 points), strength (25 points) and range of motion: forward elevation, external rotation, abduction and internal rotation of the shoulder (40 points). The higher the score, the higher the quality of the function. Once calculated, the scores are adjusted or normalized for gender and age using Constant's normative data. This normative data is reported by both Constant [1] and Katolik [2]. We will follow the original method described by Constant as Katolik incorrectly identifies categories of age.

The Oxford Shoulder Score (OSS) is a patient-based questionnaire used to assess shoulder pain after surgery. It consists of 12 questionnaire items with 5 ordinal response options for each question. Each response is scored from 0 to 4 points (4 = best/least problems). All item scores across 12 questions are summed to produce scale 0–48 (48 = best/least problems).

The EQ-5D-5L consists of the EQ-5D-5L descriptive system and the EQ Visual Analogue scale (EQ VAS). The descriptive system comprises 5 dimensions (mobility, self-care, usual activities, pain/discomfort, and anxiety/depression). And each dimension has 5 levels: no problems, slight problems, moderate problems, severe problems, and extreme problems. When a summary score is used across dimensions, each combination is mapped onto a value score. A specific mapping algorithm is used with country-specific values (U.S. values will be used for Canadian patients) [3].

6. Levels of Significance

Only the primary objective for the endpoint of device success is prospectively powered and will be conducted with a one-sided test of $\alpha = 0.025$, or equivalently, whether the lower bound of the 95% confidence intervals is above the maximum value under the null hypothesis. Confidence intervals (two-sided 95%) and p-values may be provided for analyses involving the primary, safety, secondary and tertiary endpoints. For safety endpoints no hypotheses will be tested, and the secondary/tertiary objectives are deemed exploratory. In light of these considerations, there will be no adjustment of significance levels because of testing multiple hypotheses. No labeling claims will therefore be made based on the analysis of safety, secondary and tertiary endpoints.

7. Analysis Sets

Analysis set definitions from the CIP appear below.

Consented/Enrolled Population: The Consented/Enrolled Population will consist of all subjects who were consented and enrolled in the study based on preliminary subject eligibility.

Safety Population: The Safety Population will consist of all subjects who were enrolled and were either implanted with the GLOBAL ICON stemless humeral component or an attempt was made to do so. Demographic data and analysis of the primary, safety, secondary and tertiary endpoints will be based on the Safety Population.

Per Protocol Population: The Per Protocol Population will consist of the subset of the Safety Population without specific protocol deviations. Based on review of subject data, the subset will exclude those patients that: 1) fail to satisfy all inclusion/exclusion criteria, 2) received a non-Global ICON humeral component or did not receive an approved DePuy Synthes glenoid system, and 3) failed to adhere to critical protocol-required restrictions and prohibitions, receipt of prohibited concomitant procedures or therapies, and severe non-compliance to protocol-specific procedures. The final Per Protocol Set will be determined prior to database hard lock and in agreement with clinical research and clinical operations. Analyses using the Per Protocol Population will be used to complement analyses based on the safety population.

8. Sample Size Justification

The sample size was determined based on the primary endpoint using the one-sample exact-test of a proportion as implemented in PROC POWER in SAS, version 9.3 or higher. For the calculation, we assume the composite success proportion at 24 months after surgery is 85% and implement a one-sided test at the 0.025 alpha-level to determine the minimal N which provides more than 80% power; this sample size is 133. To accommodate potential 15% attrition, the sample size will be increased to 157.

The sample size applies to patients enrolled and actually treated. Some patients who were enrolled in a study may not be ultimately treated for various reasons. Patient enrolment will continue until the proposed sample size for treated patients is complete.

NOTE: Although the sample size was originally determined based on the anticipated use of a one-sample exact-test of a proportion, it has been determined after enrolment was

complete that a one-sample Z-test of a proportion using a normal approximation would be utilized in the final primary endpoint analysis to facilitate data imputation methods.

9. Analyses to be Conducted

9.1 Descriptive Analyses

Study data will be tabulated for all subjects in the Safety Population using SAS version 9.4 or higher. Planned tabulations are described below and table, figure, and listing shells are provided separately (see Appendix).

Standard descriptive summaries for continuous data include the number of subjects with nonmissing data (n), mean, standard deviation (SD), median, minimum, and maximum values. For categorical data, the count and percentage will be provided. Percentages will be based on the number of subjects without missing data.

9.2 Disposition of Study Subjects

An overall summary of the number of subjects who were (or had): Enrolled, Enrolled but not treated, in the Safety Set, in the Per Protocol Set, withdrew before study completion, and who completed the study will be tabulated for all sites combined. A listing will be created for completion status and will include columns for all the items included in the summary table.

9.3 Demographic and Baseline Characteristics

Descriptive statistics will be displayed using the subjects in the Safety and the Per Protocol Analysis Populations for:

- Age at consent (in years)
- Gender
- Race
- Ethnicity
- Height (cm)
- Weight (kg)

- Body Mass Index (BMI) calculated as (Weight in kilograms)/(Height in meters)²
- Primary Diagnosis

9.4 Hypothesis Testing of Primary Endpoint

The primary endpoint analysis will seek to demonstrate that at the 24 month visit after surgery, the composite success (p), which is based on four study outcomes (radiograph demonstrating no continuous radiolucent line around the humeral component, adjusted Constant-Murley Score > 85, no removal of the humeral component, no serious adverse events related to the device), is significantly greater than a performance goal (PG) of 75%. The null and alternative hypotheses for this endpoint are as follows:

Null hypothesis H_{01} : $p \leq 75\%$

Alternative hypothesis H_{A1} : $p > 75\%$

The null hypothesis will be rejected and the alternative hypothesis will be accepted if the lower bound of a two-sided 95% confidence interval is greater than 75%. The performance goal of 75% used in the hypothesis test described above is based on the percentage of successful stemmed implants at the 24 month visit reported elsewhere using a similar definition of success [4]. Therefore, the hypothesis test implies a comparison to performance of stemmed implants. In a prior study, non-inferiority of the Simpliciti stemless humeral device to stemmed devices was demonstrated using a PG of 65% (75%-10% non-inferiority margin) [4]. Therefore, the current study sets a higher bar to establish successful performance of Global Icon when compared to the study evaluating the Simpliciti device.

Another objective using the same endpoint is to establish non-inferiority of Global Icon to Simpliciti conditional on rejection of H_{01} . To do so a PG or non-inferiority margin of 78.74% (Simpliciti success percentage of 88.74% [5] -10%) is selected. The null and alternative hypotheses for this objective are as follows:

Null hypothesis H_{02} : $p \leq 78.74\%$

Alternative hypothesis H_{A2} : $p > 78.74\%$

The null hypothesis will be rejected and the alternative hypothesis will be accepted if the lower bound of a two-sided 95% confidence interval is greater than 78.74%. Notably,

simultaneous testing of these nested null hypotheses (H_{01}, H_{02}) does not inflate the Type I error rate [6,7].

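### SAP 9.4 presents H02 as non-inferiority to a named stemless device, but the test can show only that success exceeds a fixed 78.74%

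*SAP*

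**What the plan says.** SAP 9.4 first tests whether composite success "is significantly greater than a performance goal (PG) of 75" per cent (H01). If H01 is rejected, it goes on: "Another objective using the same endpoint is to establish non-inferiority of Global Icon to Simpliciti". The threshold is built from "Simpliciti success percentage of 88.74" per cent, less 10 points, giving 78.74%; the SAP calls this figure either a performance goal or a non-inferiority margin. H02 is then written as p ≤ 78.74% and rejected if the lower limit of a two-sided 95% interval for p lies above 78.74%.

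SAP 9.5 describes these as one-sample tests, with the variance taken from this study's proportion by normal approximation and combined over imputations. The 88.74% is referenced to a single earlier study of the other device. Neither document gives that study's sample size, standard error or confidence interval. On error rates, SAP 9.4 says that testing the two nested hypotheses "does not inflate the Type I error rate".

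H02 appears only in the SAP. Protocol 7.6 tests 75% alone, and the sample size was set for 75%.

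**The concern.** Non-inferiority to a named device is a statement about a difference: this device's true success rate is no more than 10 points below the other's. The test concerns one rate against a constant. The two coincide only if the other device's true rate is exactly 88.74%, and that figure comes from a finite study. A team following SAP 9.4 as written could reject H02 and report a comparative conclusion at a nominal 2.5% that the test does not deliver.

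The wording matters because Protocol 7.10 plans an analysis of the primary endpoint to support a US marketing application. The SAP's statement in Section 6 that no labelling claims will be made names the safety, secondary and tertiary endpoints; H02 uses the primary endpoint.

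**Working it through.** **Inputs from the documents.** Primary goal 75% and H02 threshold 88.74 − 10 = 78.74% (SAP 9.4). For sample size (SAP Section 8): "we assume the composite success proportion at 24 months after surgery is 85" per cent, and "implement a one-sided test at the 0.025 alpha-level to determine the minimal N which provides more than 80% power"; "this sample size is 133", raised to 157 for 15% attrition. One-sample normal-approximation interval (SAP 9.5).

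**Assumed input.** The comparator's sample size N. If 88.74% is a simple proportion rounded to two decimals, the smallest possible N is 151 (134/151). I show N = 151, 300 and 500; the upper end is arbitrary.

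**1. The plan's own figures.** For 75% against 85%, the exact test at n = 133 rejects at 110 or more successes, with one-sided error 0.0223 and power 0.808. (n = 132 already gives 0.818; the z formula with null variance gives 132.07, rounded up to 133.) Then 133/0.85 = 156.5, rounded up to 157. The stated figures stand.

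**2. H02 as a fixed-goal test, n = 157.** The smallest passing count is 133/157 (84.7%). If p is exactly 78.74%, the chance of 133 or more is 3.8%. The excess over 2.5% comes from the normal-approximation interval, not from the comparator.

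**3. H02 as a comparative claim, normal form.** Let the comparator's true rate be 88.74% and this device's 78.74%, exactly 10 points worse. Let V_T be the variance of this study's proportion and V_S that of the comparator's estimate.

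- V_T = 0.7874 × 0.2126 / 157 = 0.001066, SE 3.27 points
- V_S = 0.8874 × 0.1126 / N
- Error = 1 − Φ(1.96 × √V_T / √(V_T + V_S))

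At N = 151, V_S = 0.000662 (SE 2.57 points), the SE of the difference is 4.16 points, 1.96 × 3.27/4.16 = 1.54, and the error is 6.2%.

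**4. The same claim, exact.** Here both counts are binomial and the planned rule is applied with the threshold at the comparator's estimate minus 10 points.

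| Assumed N | SE of difference (points) | Error, normal form (nominal 2.5%) | Error, exact (3.8% for a fixed goal) |
|---|---|---|---|
| 151 | 4.16 | 6.2% | 7.8% |
| 300 | 3.74 | 4.4% | 5.8% |
| 500 | 3.56 | 3.6% | 5.0% |

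The normal-form column isolates the comparator's variance. The exact column also carries the interval's own excess. With 133 subjects instead of 157, the normal-form errors are 5.6%, 4.1% and 3.4%; the exact ones are 7.0%, 5.6% and 5.0%, against 4.6% for a fixed goal.

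**5. What the average hides.** Hold the threshold at 78.74% and n at 157. If the comparator's true rate is 86.74%, a device 10 points worse (76.74%) passes 0.9% of the time. If it is 93.8%, the upper 95% limit at N = 151, a device 10 points worse (83.8%) passes about 43% of the time.

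**6. Including the comparator's variance.** With the comparator held at 88.74%, the smallest passing count rises from 133/157 to 136/157 at N = 151, and to 134/157 at N = 300 or 500. The exact error of the two-sample rule is 2.7% at N = 151 and 3.1% at N = 300. With the comparator's estimate random and both true rates 88.74%, power is:

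| Assumed N | SAP rule | Two-sample interval |
|---|---|---|
| 151 | 90% | 79% |
| 300 | 92% | 88% |
| 500 | 94% | 91% |

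**The case against.** The strongest reply is that H02 is written as p ≤ 78.74%, so no comparator variance belongs in its interval. That is right. A reader might infer that the planned interval is too narrow; for the hypothesis as written it is not. A reader might also infer that the SAP's nested-testing statement is wrong; for two fixed thresholds it is correct, and it makes no claim about the comparator's sampling error.

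A second reply is that fixed performance goals are accepted practice. That also stands, and it determines the remedy: the permitted conclusion is that the goal was exceeded. It does not rescue the sentence that names non-inferiority to a device as the objective.

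A third is that the size rests on an unseen N and on averaging over repeats of a completed study. Both limits are real. They affect the size, not the fact that a one-sample test leaves out a source of error for any finite N.

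Finally, H02 is tested only after H01 and cannot alter it, and no passage says that a labelling claim will rest on H02. That the labelling restriction in SAP Section 6 leaves H02 out is an inference from silence. The remark that for H01 "the hypothesis test implies a comparison to performance of stemmed implants" is interpretation, not a formal objective, and nothing here measures it.

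**Conclusion.** The point holds as a mismatch between the stated objective and the test. Rejecting H02 supports the statement that composite success exceeds 78.74%; it does not support non-inferiority to the named device at one-sided 2.5%.

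Assuming N = 151 to 500, 157 subjects with complete outcomes and a comparator true rate of 88.74%, ignoring the comparator's variance raises the average error of the comparative claim from 2.5% to about 6.2%–3.6% (normal form), or from 3.8% to about 7.8%–5.0% (exact).

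It is tempting to set the exact figures against 2.5% and report two to three times the nominal error. That comparison charges the interval's own excess to the comparator. The comparator's share in the exact figures is a factor of about 2.0 at N = 151 (7.8/3.8), 1.5 at N = 300 and 1.3 at N = 500. H01 as a fixed-goal test is unaffected.

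**What to change.** Restate H02 in SAP 9.4 as a test that composite success exceeds a fixed performance goal of 78.74%. Remove the non-inferiority wording from the objective and from any conclusion drawn from it. The 88.74% and the 10 points can stay as the rationale for the goal. This costs SAP wording only; the rule, the sample size and H01 do not change.

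If the comparative wording is kept, state the comparator's N from the cited source, test the difference against −10 points with an interval that includes both variances, and describe the result as an unadjusted cross-study comparison. Adding the variance does not make the two study populations comparable. The cost is power: at a true 88.74% for both devices, it falls from about 90–94% to about 79–91% for N = 151 to 500.
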